## 5.4 Primary endpoints analyses

### 5.4.1 Definition of endpoints

Two primary endpoints are considered:

- IGA 0/1 at Week 16: obtaining an IGA score of 0 (clear) or 1 (almost clear) at Week 16.
- EASI75 at Week 16: obtaining at least 75% reduction in EASI score at Week 16 relative to baseline.

Both endpoints are binary and take the values '1' (response) and '0' (non-response) depending on whether the condition is met.

### 5.4.2 Primary analyses

The primary endpoints (IGA 0/1 at Week 16 and EASI75 at Week 16) will be analysed using the composite estimand strategy to handle the occurrence of intercurrent events (initiation of rescue medication or permanent discontinuation of IMP).

Missing data for subjects who do not attend the Week 16 visit and where rescue medication has not been used, nor the subject has permanently discontinued IMP, will be imputed as non-response.

The number and percentage of subjects achieving response will be presented together with the corresponding 95% CI.

The analysis will be based on the FAS.

THIS DOCUMENT CONTAINS CONFIDENTIAL INFORMATION AND MUST NOT BE COPIED OR MADE AVAILABLE TO ANY THIRD PARTY WITHOUT THE PRIOR WRITTEN CONSENT OF THE LEO PHARMA GROUP

## 5.5 Secondary and other endpoints analyses

The secondary endpoint, number of treatment-emergent AEs from baseline up to Week 16, and the analysis of this is covered in Section [5.7.1](#).

The secondary endpoint, presence of treatment-emergent ADA from baseline to Week 16, and the analysis of this is covered in Section [5.6](#).

### 5.5.1 Successful subject self-administration

The subject's ability to self-administer tralokinumab using the autoinjector will be assessed following each administration after baseline (Week 0). The assessment is based on the defined sequence of use steps described in CTP section 11.3 and as outlined in [Panel 5](#).

Successful subject self-administration for administration at trial site or following dosing at home is defined as completion of each defined sequence of use steps without errors. Each step is recorded in the eCRF.

[Panel 5](#) shows the combination of answers that constitutes a successful self-injection. For all other combinations of answers, the self-administration is defined as unsuccessful.

#### Panel 5: Successful subject self-administration

Question in eCRF	Answer corresponding to errorless completion
Did the subject choose the correct injection area?	Yes*
Did the subject remove the cap?	Yes
Did the subject press device down to begin injection?	Yes
Did the subject hold until the injection is complete?	Yes
Did the yellow plunger cover the viewing window completely when removing the autoinjector from the injection area?	Yes
Was liquid dripping from the tip of the autoinjector when removing it from the injection area?	No

\*) The injection area is considered correct if the subject chose left or right anterior thigh, or abdomen.

**Abbreviations:** eCRF = electronic case report form.

THIS DOCUMENT CONTAINS CONFIDENTIAL INFORMATION AND MUST NOT BE COPIED OR MADE AVAILABLE TO ANY THIRD PARTY WITHOUT THE PRIOR WRITTEN CONSENT OF THE LEO PHARMA GROUP

The number and percentage of subjects with successful IMP self-administration when observed in clinic at Week 4 will be presented together with the corresponding 95% CI (based on the Wilson method). Subjects who permanently discontinue IMP before Week 4 and subjects with missing values will be excluded from the analysis.

The analysis will be based on the usability analysis set.

The successful IMP self-administration when administered at home at Week 8, will be analysed in the same way as for the endpoint at Week 4 with the modification that subjects must not have permanently discontinued IMP prior to Week 8.

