14.3 Statistical analysis

All results will be presented for the total cohort of subjects as well as for adults and adolescents, separately.

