14.3.9 Analysis of other endpoints related to subject self-administration

The number and percentage of subjects with successful IMP self-administration when observed in clinic at Week 4 will be presented together with the corresponding 95% CI. The analysis will be based on the population of subjects who have been trained on the usage of the autoinjector by the investigator or delegated trial staff, have tried self-injection at least once, and have not permanently discontinued IMP prior to Week 4. Subjects with missing data at Week 4 will be excluded from the analysis.

The successful IMP self-administration when administered at home at Week 8, will be analysed in the same way as for the endpoint at Week 4 with the modification that subjects must not have permanently discontinued IMP prior to Week 8.

All data captured to assess subject's ability to self-administer tralokinumab using the autoinjector will be presented descriptively as observed by week.

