Appendix 8: COVID-19 pandemic contingency plan

Without compromising the safety of subjects and trial integrity, it is expected that efforts are made to secure attendance at sites for all visits, ensuring important efficacy and safety assessments for the trial.

If on-site visits are not possible due to local authority-issued preventive measures or subjects are unwilling to come to the trial site or are quarantined at home, the affected site will postpone screening and baseline visits of subjects until on-site visits can be conducted. Furthermore, it is a requirement that all subjects attend the first 3 dosing visits (Weeks 0, 2, and 4, i.e. Visits 2, 3, and 4) at the clinic according to protocol to ensure the 30 min. post-dose observation time for the 3 dosing visits. The primary endpoint of the trial, efficacy of tralokinumab administered by an autoinjector, will be assessed at the clinic at Week 16. If attending the first 3 dosing visits is not possible, then the subject cannot self-administer IMP at home during the remainder of the trial.

For subjects already assigned to treatment, Week 12 (Visit 8) can be done remotely via phone or video. At phone/video visits, no investigator assessments of efficacy will be done, but the following data will be collected remotely (according to the schedule of trial procedures in Section 4):

- Use of emollients
- AE reporting.
- Concomitant medication and concurrent procedures.
- PROs (DLQI/CDLQI, POEM, Eczema-related Sleep NRS, Worst Weekly Pruritus NRS/Adolescents Pruritus NRS). The subjects will receive a link to complete the PROs in a web browser.
- Urine pregnancy test. Women of childbearing potential will receive 1 extra urine pregnancy test at the baseline visit to keep at home in case on-site visit becomes impossible during the trial. The subject will perform the test at home and inform the investigator about the result via phone before self-administering the IMP.

In the eCRF, it will be recorded whether a visit or a given assessment was done remotely or not done. If not done, it will be recorded in the comments log if this was due to the COVID-19 pandemic.

THIS DOCUMENT CONTAINS CONFIDENTIAL INFORMATION AND MUST NOT BE COPIED OR MADE AVAILABLE TO ANY THIRD PARTY WITHOUT THE PRIOR WRITTEN CONSENT OF THE LEO PHARMA GROUP

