## 1 Introduction

The statistical analysis will be performed as outlined in the CTP version 3.0. This SAP, prepared before database lock, supplements the CTP, and contains a more technical and detailed elaboration of topics related to the specification and implementation of the statistical analysis described in the CTP. The level of detail should enable the reader to reproduce all statistical analyses described in the SAP and the CTP.

Changes to the protocol-planned analyses are described/summarised in Section 6, while supplementary analysis specifications are elaborated in the individual sections.

Data handling decisions and derivation rules used in the analysis datasets are specified in the analysis data reviewer's guide (ADRG) and Data Definition document (define.xml).

THIS DOCUMENT CONTAINS CONFIDENTIAL INFORMATION AND MUST NOT BE COPIED OR MADE AVAILABLE TO ANY THIRD PARTY WITHOUT THE PRIOR WRITTEN CONSENT OF THE LEO PHARMA GROUP

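### Can an injection form that records a use error drop out of the Week 4 and Week 8 self-administration rates because another item is blank?

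*SAP*

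**What the plan says.** Protocol 11.3 lists the use steps and has the site record, for each step, whether the subject could perform it. SAP 5.5.1 turns this into six eCRF questions (Panel 5) with one pattern of answers that counts as success. For everything else: "For all other combinations of answers, the self-administration is defined as unsuccessful". After Panel 5 the SAP limits the Week 4 analysis: "Subjects who permanently discontinue IMP before Week 4 and subjects with missing values will be excluded from the analysis". Week 8 is analysed the same way, with the discontinuation cut-off moved to Week 8.

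Protocol 14.3.9 has the parent rule: "Subjects with missing data at Week 4 will be excluded from the analysis". It also promises that all data on the subject's ability to self-administer "using the autoinjector will be presented descriptively as observed by week". SAP Panel 11, which lists departures from the protocol, has no entry for Section 14.3.9.

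Three further statements bear on the point. The SAP introduction says: "The level of detail should enable the reader to reproduce all statistical analyses described in the SAP and the CTP". The same section places derivation rules for the analysis datasets in the reviewer's guide and define.xml. SAP 5.1.1 sends the handling of missing post-baseline values to the individual analysis sections. Protocol 14.3 adds: "All results will be presented for the total cohort of subjects as well as for adults and adolescents, separately".

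**The concern.** The two sentences in SAP 5.5.1 can be read so that they overlap. Take a form on which one item is answered as an error and another is left blank. It cannot match Panel 5, so it is unsuccessful. It also contains a missing value, so the subject could be excluded. No sentence says which rule comes first, or whether missing means any blank item, all items blank, or an outcome that cannot be determined. SAP 5.1.1 points to this very section for the answer, and the SAP sets itself a standard of reproducibility, so two programmers working from the text alone could report different rates.

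If the form is dropped, a known failure leaves both the failure count and the denominator, and the rate can only go up. These are the only two endpoints for the objective on patient handling of the autoinjector, and the adolescent group is small enough for one form to show.

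A second strand is that subjects with no rating at all also leave the denominator, with no supportive rate that counts them as failures.

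**Working it through.** **Inputs.** About 130 subjects, of whom about 30 are adolescents (SAP 3). Wilson 95% intervals (SAP 5.5.1). No expected success rate, missing rate or precision is given for these endpoints, so every count of forms below is an assumption. The only precision figures in the documents are for the primary endpoints (Protocol 14.1), and they reproduce at n = 130:

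- √(0.19 × 0.81/130) = 3.44%, half-width 1.96 × 3.44% = 6.74%
- √(0.29 × 0.71/130) = 3.98%, half-width 1.96 × 3.98% = 7.80%

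**Step 1: the text.** Success requires all six answers to be as in Panel 5. One wrong answer rules that out whatever the blank item would have been. The outcome is therefore known, and it is unsuccessful.

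- The exclusion sentence in SAP 5.5.1 is about subjects. It sits beside permanent discontinuation, which is a subject-level condition.
- Protocol 14.3.9 speaks of subjects with missing data at the week in question, and Panel 11 declares no change to that rule.
- SAP 5.5.2, the next section, imputes missing values as non-response where no intercurrent event has occurred. There the term can only mean a missing endpoint value.

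Read together, the outcome is derived first, and only subjects whose outcome cannot be derived are excluded. The overlap then disappears.

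**Step 2: does the pattern arise?** Because Protocol 11.3 records whether or not each step could be performed, a step that was not performed is answered no and is not left blank. Protocol Appendix 3D provides automatic and manual queries on discrepant data. Blanks remain possible, but nothing in the documents indicates that error forms with a blank item are expected.

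**Step 3: size if the literal reading were used.** With F error forms among N, of which k are dropped for a blank item, the rate moves from (N − F)/N to (N − F)/(N − k). The Wilson interval, with p the rate, n the denominator and z = 1.96, is [p + z²/2n ± z√(p(1 − p)/n + z²/4n²)]/(1 + z²/n).

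| N | F | k | Counted as failure | Dropped |
|---|---|---|---|---|
| 130 | 4 | 1 | 126/130 = 96.9% (92.4 to 98.8) | 126/129 = 97.7% (93.4 to 99.2) |
| 130 | 4 | 2 | 126/130 = 96.9% (92.4 to 98.8) | 126/128 = 98.4% (94.5 to 99.6) |
| 130 | 5 | 5 | 125/130 = 96.2% (91.3 to 98.3) | 125/125 = 100% (97.0 to 100) |
| 30 | 1 | 1 | 29/30 = 96.7% (83.3 to 99.4) | 29/29 = 100% (88.3 to 100) |
| 30 | 3 | 1 | 27/30 = 90.0% (74.4 to 96.5) | 27/29 = 93.1% (78.0 to 98.1) |

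Over N = 120 to 130, F = 2 to 6 and k = 1 to 2, the smallest shift is 124/130 = 95.4% to 124/129 = 96.1% (0.7 points) and the largest is 118/120 = 98.3% to 118/118 = 100% (1.7 points). The third row, where every failure has a blank item, gives 3.8 points and is an extreme case. With k = 0 there is no shift.

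**Step 4: the one-sidedness is assumed.** Step 3 puts blanks only on error forms. If success forms also have blanks, keeping error forms while excluding undetermined ones is not neutral either. With N = 30, 2 errors and 3 error-free forms with a blank, it gives 25/27 = 92.6%, against 28/30 = 93.3% had all items been completed.

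**Step 5: unrated subjects.** Counting them as failures answers a different question. With N = 120, 2 failures and 8 unrated, the rate goes from 110/112 = 98.2% to 110/120 = 91.7%. The 6.5-point gap comes entirely from treating an absent rating as a handling error. Some absences have nothing to do with handling: under Protocol Appendix 8, if the first three dosing visits cannot be attended, "then the subject cannot self-administer IMP at home during the remainder of the trial". The same appendix says of the eCRF that "it will be recorded whether a visit or a given assessment was done remotely or not done", so missed assessments can be identified without imputing them.

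**The case for a change.** The strongest case for acting is that error forms with blanks are mechanically plausible. The steps are sequential. If the injection never starts, the items on the plunger and on dripping may have nothing to describe and could be left empty. Protocol 11.3 adds that when a new autoinjector is assigned because no dose was received, the replacement injection is not rated, so the failed form is the only rating for that administration. Under the literal reading, the most serious use errors would be the ones to vanish. Writing the rule down would take a sentence or two, and SAP 5.1.1 says the rule belongs in this section.

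Much of this stands. The SAP does not define the term, and a definition would have been tidy. But the argument needs an analyst to see a recorded failure and treat the outcome as unknown, against the sentence in the same section that classifies it as unsuccessful. The dataset specifications that the SAP names are also an ordinary home for item-level rules of this kind; they are not among the documents, so whether they contain one is unknown. Item-level answers are to be shown by week in any case. That display would not correct a wrong rate, but a reader could see the error.

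On unrated subjects, the exclusion is prespecified in Protocol 14.3.9 and the SAP follows it. A rate counting them as failures would be a matter of preference. If it were limited to subjects who had tried self-injection at least once, as Protocol 14.3.9 requires, it would use a condition that is absent from the SAP's usability analysis set, so it would not share a population with the main rate.

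**Conclusion.** No change to the plan is needed. This is missing detail that a competent analyst fills correctly from the surrounding text: a form with any recorded error is unsuccessful and stays in the denominator, and exclusion applies where the outcome cannot be determined or no form exists.

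The effect is nil if no error form has a blank item. Under the assumed counts, the wrong reading would overstate the overall rate by 0.7 to 1.7 points, and the adolescent rate by about 3 points per form. Neither the primary efficacy results nor the secondary safety results are touched. The two endpoints support an objective listed among the other objectives, with no formal testing and no success threshold. Excluding unrated subjects is a fair, prespecified choice, and a worst-case rate would mix absent ratings with handling failure.

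The conclusion rests on two things: reading missing values at endpoint level, as SAP 5.5.2 does, and steps not performed being recorded as such, as Protocol 11.3 requires.

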9.8.4 Treatment compliance

At site visits, site staff will keep the accountability records up to date. Any non-compliance and the reason for it must be recorded in the eCRF.

Where IMP is injected by the subject at the trial site, the site staff will record compliance data in the eCRF.

Where IMP is injected by the subject at home, the subject or subject's caregiver will record the date and injection site for each administration in a log of drug administration; these data will be transcribed into the eCRF by site staff at the next site or telephone visit. If a subject is found to be non-compliant, the investigator should remind the subject of the importance of following the treatment instructions including taking the IMP as prescribed. Any non-compliance and the reason for it must be recorded in the eCRF.

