11.3 Rating of subject's ability to self-administer

The subject's ability to self-administer tralokinumab using the autoinjector will be assessed following each administration after baseline (Week 0). The assessment is based on the defined sequence of use steps:

- 1) Choose the correct injection area.
- 2) Remove the cap.
- 3) Press device down to begin injection.
- 4) Hold until the injection is complete.
 - Was the dose completed?
 - i. Did the yellow plunger cover the viewing window completely when removing the autoinjector from the injection area?
 - ii. Was liquid dripping from the tip of the autoinjector when removing it from the injection area?

For the self-administrations performed at the trial site (Weeks 2, 4, and 12), the observer (investigator or delegated trial staff) will assess the subject's ability to self-administer.

THIS DOCUMENT CONTAINS CONFIDENTIAL INFORMATION AND MUST NOT BE COPIED OR MADE AVAILABLE TO ANY THIRD PARTY WITHOUT THE PRIOR WRITTEN CONSENT OF THE LEO PHARMA GROUP

For the self-administration performed at home (Weeks 6, 8, 10, and 14), the subjects will assess their ability to self-administer based on the defined sequence of use steps.

Successful subject self-administration for administration at trial site or following dosing at home is defined as completion of each of the above defined sequence of use steps without errors.

It will be recorded in the eCRF whether or not the subject could perform each of the defined sequence of use steps.

If a new autoinjector is assigned due to errors resulting in the subject not receiving any of the intended dose, the assessment of subject ability to self-administer should not be made for the new injection.

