### Panel 2: Trial analysis sets

Trial analysis set	Description and purpose
Full analysis set (FAS)	
 
• All subjects assigned to treatment and who received at least 1 dose of IMP.
 
• The FAS is used to analyse endpoints related to the efficacy objectives
 

Safety analysis set (SAF)	
 
• All subjects assigned to treatment and who received at least 1 dose of IMP.
 
• The SAF is used to analyse the endpoints and assessments related to safety, PK and ADA during the treatment period.
 

Usability analysis set	
 
• All subjects assigned to treatment, who received at least 1 dose of IMP and have been trained in the usage of the autoinjector by investigator or delegated staff at the baseline visit.
 
• Usability analysis set will be used to analyse objectives related to subject self-administration.
 

Safety follow-up (SFU) analysis set	
 
• All subjects for whom date of last contact is after the date of exposure end, where exposure end is defined as the date of week 16 visit for subjects completing the treatment period, and otherwise the date of permanent discontinuation of IMP for subjects not completing the treatment period.
 
• SFU analysis set is used to analyse endpoints and assessments related to safety during the SFU period.
 

**Abbreviations:** IMP = investigational medicinal product

THIS DOCUMENT CONTAINS CONFIDENTIAL INFORMATION AND MUST NOT BE COPIED OR MADE AVAILABLE TO ANY THIRD PARTY WITHOUT THE PRIOR WRITTEN CONSENT OF THE LEO PHARMA GROUP

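### The Week 4 and Week 8 self-administration rates leave out unrated doses and subjects who stopped IMP, so they may overstate how well subjects handle the autoinjector

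*SAP*

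**What the plan says.** For Week 4, the text under Panel 5 in SAP 5.5.1 states: "Subjects who permanently discontinue IMP before Week 4 and subjects with missing values will be excluded from the analysis". Week 8 is handled identically, "with the modification that subjects must not have permanently discontinued IMP prior to Week 8". Protocol 14.3.9 agrees on missing ratings: "Subjects with missing data at Week 4 will be excluded from the analysis". It also limits the population to trained subjects who "have tried self-injection at least once, and have not permanently discontinued IMP prior to Week 4".

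The SAP analyses these endpoints on the usability analysis set (SAP Panel 2): dosed subjects who "have been trained in the usage of the autoinjector by investigator or delegated staff at the baseline visit". That set does not require a previous attempt at self-injection. SAP Panel 11 presents it as the protocol's population given a name and does not mention the difference.

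Failed attempts are covered. Protocol 11.3 says "It will be recorded in the eCRF whether or not the subject could perform each of the defined sequence of use steps", and SAP 5.5.1 adds "For all other combinations of answers, the self-administration is defined as unsuccessful".

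On doses not taken as planned, Protocol 9.8.4 says "Any non-compliance and the reason for it must be recorded in the eCRF". Neither document plans a sensitivity analysis for the excluded subjects, or a count of those exclusions by whether handling was the cause.

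**The concern.** The rating is made after an administration (Protocol 11.3, SAP 5.5.1), so a due dose that nobody attempted produces none. Self-administration is mandatory after Visit 2 (Protocol 12.1), so a subject who cannot or will not inject has no planned alternative and may well miss the dose or stop IMP. Either way the subject leaves the denominator, and the endpoint becomes success among those who made a rated attempt.

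The objective in Protocol section 6 is to learn how patients manage the device in everyday use, and for that a failure to inject at all is relevant. Entry is already restricted to subjects judged able and willing to self-inject (inclusion criterion 4), so the exclusion may act as a second filter in the same direction. Week 8 is more exposed than Week 4: the rating is self-reported at home, and more subjects will have stopped by then.

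Protocol 14.3.6 promises that these endpoints will follow ICH E9(R1) principles, including the intercurrent-event attribute, but neither document names a strategy for discontinuation or a missed dose here.

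**Working it through.** **The plan's own figures.** Protocol 14.1 gives precision for the primary endpoints only. With SE = √(p(1−p)/130) and half-width 1.96 × SE:

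- p = 19%: SE 3.44%, half-width 6.74%.
- p = 29%: SE 3.98%, half-width 7.80%.

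Both agree with the protocol. It gives no such figure for self-administration.

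**Who leaves the denominator.**

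| Situation at Week 4 or 8 | Rated? | In the analysis? |
|---|---|---|
| Attempted, all steps correct | Yes | Yes, successful |
| Attempted, any step wrong | Yes | Yes, unsuccessful |
| Replacement device after an error that delivered no dose | Not re-rated (Protocol 11.3) | The replacement cannot add a success |
| Due dose never attempted | No | Excluded as missing |
| IMP permanently stopped earlier, any reason | No | Excluded |

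**Size.** Let s be the success rate among rated subjects, f the share excluded, and g the rate at which excluded subjects would have succeeded. The rate over everyone is s(1−f) + g·f, so the available-case rate overstates it by f(s−g). This is zero when g = s and reaches its maximum, s·f, when g = 0.

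The documents give neither s nor f. Assumed: N = 130 (the planned size), s from 85% to 98%, f from 3% to 15%. Using whole subjects:

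| Excluded of 130 | Maximum overstatement (points) |
|---|---|
| 4 (about 3%) | 2.6-3.0 |
| 6 (about 5%) | 3.9-4.5 |
| 13 (10%) | 8.5-9.8 |
| 20 (about 15%) | 13.1-15.1 |

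**One case in full**, with 95% Wilson intervals as in SAP 5.1. With 13 excluded and 111 of 117 rated successful, the planned analysis reports 94.9% (89.3-97.6). With all 13 counted as failures, 111/130 = 85.4% (78.3-90.4). If half of the 13 would have succeeded, (111 + 6.5)/130 = 90.4%, so the overstatement is 94.9 − 90.4 = 4.5 points.

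**Adolescents**, who are reported separately (Protocol 14.3). With 3 of 30 excluded, 26/27 = 96.3% (81.7-99.3) against 26/30 = 86.7% (70.3-94.7) in the worst case.

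**What the fixed table would show**, for an invented split of 120 successful, 2 unsuccessful and 8 unrated, with 4 of the 8 unrated for handling reasons:

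- Observed cases: 120/122 = 98.4% (94.2-99.5).
- Handling-related cases counted as unsuccessful: 120/126 = 95.2% (90.0-97.8).
- Worst case: 120/130 = 92.3% (86.4-95.8).

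**The differing population definitions.** Under the SAP, a trained subject who never attempts an injection enters the usability set and is then removed as missing. Under the protocol that subject is never in the population. The subjects analysed are therefore the same today. The difference starts to matter once unattempted doses count as unsuccessful.

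**The case against.** The strongest reply is that the main form of usability failure is already captured. A subject who attempts the injection and gets a step wrong is rated, counted as unsuccessful and kept, and a replacement device cannot rescue the result. A reader might infer that subjects who could not use the autoinjector generally vanish from the analysis. The documents do not support that; it applies only where there was no rated attempt. Nor do they support the inference that a dose given by another person always goes unrated, since nothing says the home questionnaire would be left blank.

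Next, exclusion need not concern the device. The stop reasons in Protocol 10.2.1 include adverse event, lack of efficacy, pregnancy and loss to follow-up. A rating can also be absent because of rescheduling for illness or fever (Protocol 9.2) or temporary suspension (Protocol 10.2.2). Counting all of these as failures would mislabel some subjects. This stands: the worst-case row is a bound, not an estimate.

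Third, the rule is prespecified, agrees across the two documents on these exclusions, and defines a legitimate quantity: success given a rated administration. Stop reasons, compliance and all self-administration data by week will be reported anyway (Protocol 14.3.1, 14.3.3, 14.3.9), so the exclusions are not hidden. This also stands, but those outputs do not connect the excluded subjects to the success rate.

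Finally, the data may not be clean enough. Protocol 9.8.4 requires a reason for non-compliance, but neither document describes coded categories for inability, refusal or who injected. Among the end-of-treatment reasons, only adverse event and other call for a specification, so a withdrawal by the subject may not reveal a handling problem. This limits the reason-based count and is why a bound is needed beside it.

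**Conclusion.** The concern holds as a risk of upward bias confined to doses never attempted and to stops caused by inability or unwillingness to self-inject. Under the assumptions above (130 subjects, 85-98% success among those rated), the overstatement is at most about 3 points with 3% excluded and 8.5-9.8 points with 10% excluded. It is zero if excluded subjects would have succeeded as often as rated ones.

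A reader might go further and conclude that the reported rate is biased. The documents do not establish that: they give no success rate, no exclusion rate and no link between exclusion and handling. A reader might also expect the trial's main conclusion to be affected. It is not. These are descriptive endpoints under the other objectives, with no formal test and no success threshold. The change is worth making because it is cheap and puts limits on a rate that otherwise depends on an untested assumption about the excluded subjects.

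**What to change.** In SAP 5.5.1, on the usability analysis set, at Week 4 and Week 8:

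1. Count as unsuccessful a due self-administration that was missed, or a permanent discontinuation before the time point, where the recorded reason (the eCRF non-compliance reason or the end-of-treatment reason) is inability, refusal or a device problem.
2. Tabulate the remaining exclusions by reason.
3. Show a worst-case row, with every missing or discontinued subject unsuccessful, beside the observed-case rate, each with its Wilson interval.
4. State that the SAP set omits the protocol's condition of at least one earlier attempt, and record this as a change in Panel 11. No SAP text needs deleting.

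The cost is revised SAP wording, one extra table row, manual review of free-text reasons under a rule fixed before the data are examined, and possibly a slightly lower reported rate. No new data collection is needed, but reasons recorded without detail will remain unclassified and will be reflected only in the worst-case row.
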